14.3.8 Analysis of pharmacodynamics and pharmacogenomics

Exploratory analyses of biomarkers will be performed for the total population as well as for subtype of chronic hand eczema and by disease severity.

A summary of the results will be included in the CTR if it is available in time for this. The full set of biomarker results will be reported in an addendum report to the CTR.

14.3.9 Analysis of safety

The analysis of safety will be based on the safety analysis set.

14.3.9.1 Adverse events

AEs will be coded during the course of the trial according to Medical Dictionary for Regulatory Activities (MedDRA). AEs will be presented by preferred terms and primary system organ class (SOC).

Treatment-emergent AEs will be summarised; however, all AEs recorded during the course of the trial will be included in subject data listings. An event will be considered treatment-emergent if started after the first use of IMP or if started before the first use of IMP and worsened in severity after first dose of IMP. The tabulations described in the following will only include the treatment-emergent events. In each of the tabulations, AEs are defined by MedDRA preferred terms within primary SOC.

An overall summary of the number of events and the number (percentage) of subjects with any treatment-emergent AEs, deaths, SAEs, premature discontinuations from the trial due to AEs, treatment-related AEs and severe AEs will be presented.

The number of AEs and number of subjects with each type of AEs will be tabulated by treatment group.

The severity for each type of AE will be tabulated by treatment group. Where there are several recordings of severity for a given type of AE, severity will be taken as the most severe recording for that AE.

The causal relationship to IMP for each type of AE will be tabulated by treatment group. Where there are several recordings of causal relationship to the IMP for a given type of AE, causal relationship will be taken as the most-related recording from the last report of that AE, since that is when the investigator will be in possession of most information and so best able to judge causal relationship.

Related AEs are defined as AEs for which the investigator has not described the causal relationship to IMP as 'not related'. The number of subjects with each type of related AE will be tabulated.

SAEs will be evaluated separately and a narrative for each will be given.

Adverse events of special interest will be tabulated by treatment group.

AEs leading to withdrawal from trial and AEs leading to permanent discontinuation of IMP will be tabulated by treatment group.

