the subjects attend the visit scheduled at Week 16. Efficacy and safety assessments during the treatment period will be performed as described in Section 11.

Follow-up period: 2 weeks

All randomised subjects will attend a follow-up visit approximately 2 weeks after the last IMP application for assessment of safety. This visit will mark the end of trial participation for subjects who have completed the entire trial. For subjects who discontinue trial treatment prematurely or withdraw from the trial, please refer to Section 10.3.

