9.5 Rescue treatment

If medically necessary (i.e., to control intolerable chronic hand eczema symptoms), rescue treatment for chronic hand eczema may be provided to the subjects at the discretion of the investigator. The investigators should make every attempt to conduct efficacy and safety assessments (for example disease severity scores, safety labs) immediately before administering any rescue treatment.

If rescue treatment is initiated, the subject must stop treatment with IMP immediately and must not re-start treatment with IMP. It must be stated in the eCRF that the subject receives rescue medication. For the purpose of the primary efficacy analyses, subjects receiving rescue treatment during the IMP treatment period will be considered as non-responders.

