10.3 Early termination assessments

An end of trial form must be completed for all subjects, including subjects who withdraw from the trial or discontinue IMP treatment, at their last trial visit (the early termination visit, the safety follow-up visit, or the primary endpoint visit, whichever comes last).

Withdrawal from trial

Subjects, who withdraw from the trial must attend an early termination visit as soon as possible after last administration of IMP (see the schedule of trial procedures [Section 4] for data to be collected at an early termination visit). The investigator will review any AEs which will be followed-up according to Section 13.7, if the subject agrees.

Discontinuation of IMP

Subjects, who discontinue IMP prior to Week 16 will be asked to attend an early termination visit as soon as possible after last IMP application and return to the trial site for 2 additional visits as indicated below. See the schedule of trial procedures (Section 4) for data to be collected at these visits.

Subjects, who discontinue IMP prior to Week 16 will be asked to attend:

- Early termination visit (as soon as possible after the last IMP application).
- Safety follow-up visit (2 weeks after the last IMP application).
- Primary endpoint visit (16 weeks after the first IMP application).

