13.2 Collection of adverse event reports

AEs must be collected from time of first trial-related activity after the subject has signed the informed consent form until completion of the clinical trial for the individual subject.

AEs must be assessed by medically qualified personnel.

At all visits/phone call, the subject will be asked a non-leading question by the investigator about AEs, for example: "How have you felt since I saw you last?" No specific symptoms should be asked for. It is important that the investigator also observes the subject for any changes not reported by the subject and records these changes. If a subject reports an AE during the phone call on Day 4, it is up to the investigator's discretion to perform an unscheduled visit.

Refer to Sections [11.4.1](#) to [11.4.4](#) for principles for data entry in the eCRF.

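### Treatment-emergent has a start but no end tied to last IMP use, so for early stoppers who stay in the trial the AE tables mix on-IMP and long off-IMP events

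*Combined protocol and SAP*

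**What the plan says.** Section 14.3.9.1 defines the term in two limbs. The first is onset: "An event will be considered treatment-emergent if started after the first use of IMP". The second covers an event that was already present and becomes more severe once dosing has begun. Neither refers to the last application or to the start of rescue. The section continues: "The tabulations described in the following will only include the treatment-emergent events". The main table follows: "The number of AEs and number of subjects with each type of AEs will be tabulated by treatment group". Severity, causality, related events and events of special interest are tabulated on the same basis. None of these tables is divided into events on and off IMP.

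Three other provisions decide how long the open end runs:

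- **AE collection.** Section 13.2 collects AEs "until completion of the clinical trial for the individual subject". The AE row of Panel 2 is marked at every visit, including the follow-up, primary endpoint and unscheduled visits.
- **Follow-up.** Section 7.1 states: "All randomised subjects will attend a follow-up visit approximately 2 weeks after the last IMP application for assessment of safety". Section 10.3 also asks subjects who stop IMP before Week 16 to return for a primary endpoint visit 16 weeks after first application.
- **Rescue.** Section 9.5 states: "If rescue treatment is initiated, the subject must stop treatment with IMP immediately and must not re-start treatment with IMP". All time on rescue is therefore off IMP.

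**The concern.** One objective is to compare the safety of each strength with vehicle. An AE table serves that purpose best when the reader knows how much of the time behind each count was spent on or shortly after the product. Here the answer varies by subject. A completer contributes 16 weeks on IMP and about 2 weeks off. A subject rescued early may contribute a few weeks on IMP and several months off it, partly on another drug, and all of it feeds the same row of the same table.

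Off-IMP events are foreseeable. Section 13.6.6 requires clinically significant worsening of the hand eczema itself to be reported as an AE, so a flare weeks after stopping is an event, as is a reaction to the rescue drug.

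The plan also treats time differently elsewhere. Section 14.3.6 drops HECSI data after IMP discontinuation or rescue, and section 14.3.3 measures exposure only to the last application. AE counts read against the exposure table would therefore cover mismatched periods.

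**Working it through.** The plan gives no figure on this point, so there is none to reproduce. The visit days come from Panel 2 and section 10.3.

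**Step 1: off-IMP time per subject.** Let L be the day of last application. The safety visit is at L + 14. For a subject who stops IMP before Week 16, the primary endpoint visit is on Day 113 (16 × 7 + 1), ±3 days. For a subject who attends both:

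off-IMP days open to a treatment-emergent event = max(L + 14, 113) − L

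| Last application | Off-IMP days | Of which beyond 14 days |
|---|---|---|
| Day 15 | 113 − 15 = 98 | 84 |
| Day 29 | 113 − 29 = 84 | 70 |
| Day 57 | 113 − 57 = 56 | 42 |
| Day 85 | 113 − 85 = 28 | 14 |
| Day 99 | 113 − 99 = 14 | 0 |
| Day 112 | 126 − 112 = 14 | 0 |

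A subject treated to Week 14 (Day 99) or beyond is unaffected. The theoretical maximum is 112 days (16 weeks), for a stop on Day 1.

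**Step 2: illustration by arm.** The documents give no stopping or rescue rates, so everything here is assumed: 50 per arm, stoppers all stop at Week 6, and all of them return. Completers are followed for 18 weeks and stoppers for 16. Time beyond the 14-day window is 16 − 6 − 2 = 8 weeks per stopper.

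| Assumed stopping | Total person-weeks | Beyond window | Share | Within window |
|---|---|---|---|---|
| 30% | 35 × 18 + 15 × 16 = 870 | 15 × 8 = 120 | 13.8% | 750 |
| 15% | 42.5 × 18 + 7.5 × 16 = 885 | 7.5 × 8 = 60 | 6.8% | 825 |
| 5% | 47.5 × 18 + 2.5 × 16 = 895 | 2.5 × 8 = 20 | 2.2% | 875 |

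The share of late off-IMP time can thus differ by arm. Total follow-up hardly does: at 30% versus 5% the gap is (895 − 870)/895 = 2.8%.

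**Step 3: does this imply a direction?** Suppose the AE rate within the window is the same in both arms, and the later rate is k times that. In within-window rate units, the 30% arm has an expected count of 750 + 120k and the 5% arm 875 + 20k. They are equal when 100k = 125, that is k = 1.25. Below 1.25 the arm with more stopping shows fewer events, and above it more. The documents give no basis for k.

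**Step 4: what would a cut-off alone do?** Counting only within-window events leaves 750 against 875 person-weeks, a gap of (875 − 750)/875 = 14.3%. Replacing the definition without showing rates would therefore make raw counts less comparable.

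**The case against.** Counting everything after first use over similar calendar time is a legitimate choice. Step 2 supports it: total follow-up is nearly equal, and Step 4 shows that a bare cut-off widens the gap. This stands, and it is why the all-events table should stay.

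The open end is also bounded in practice. Collection stops at the subject's last visit, and a subject who withdraws from the trial is required by section 10.3 to attend only an early termination visit. After the 2-week safety visit, an early stopper has one further scheduled visit, so late events may be under-recorded. These points narrow the problem to early stoppers who remain in the trial, but do not remove it.

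The causality and related-AE tables, SAE narratives and listings help. However, the overall and severity tables are not restricted by causality, and listings give no comparison between groups.

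The 14-day interval is when a visit is scheduled; the protocol does not define it as a risk period. It is a convenient internal reference and no more.

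Finally, section 14.3.12 leaves the SAP to be finalised before unblinding, so an end could still be set. None appears in the text provided.

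A reader might infer that vehicle, with more rescue, would absorb extra events and make the active strengths look safer. The documents do not support that. They give no rescue, stopping or AE rates by arm; early stopping could be commoner on an active strength; and Step 3 shows that even the sign depends on an unknown rate ratio.

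**Conclusion.** The point holds as a matter of classification. As written, the rule labels events 14 weeks or more after last IMP as treatment-emergent, including any on rescue, and no planned table lets a reader see them apart. It affects only subjects who stop IMP before Week 14 and stay under observation, and makes no difference for completers.

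If stopping or rescue differs by arm, the strength-versus-vehicle comparison mixes exposed and unexposed time unequally. How many events this touches, and which way it moves the comparison, cannot be determined from the documents. The 13.8%, 6.8% and 2.2% shares rest on assumed stopping rates, a single stop time and full return, and are illustrations only. The primary endpoint is not involved. This is a cheap improvement to the safety reporting, worth making before unblinding.

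**What to change.** In section 14.3.9.1 or the SAP, keep the table of all events after first IMP use and add by-group AE tables in two parts:

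- (a) onset or worsening from first IMP application to 14 days after last IMP application;
- (b) later onset or worsening.

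Flag events with onset after the start of rescue. For each part, show person-time and events per person-time, because the window length differs by arm. State whether treatment group in the safety set means as randomised or as treated, since the text does not say.

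The cost is one extra table set. AE start dates (section 13.3), the date of last application (section 11.9) and medication start dates (section 9.6) are already collected, and a worsened AE is recorded as a new one (Appendix 2). No visit or procedure changes. The drawback is that window (a) is shorter in arms with more early stopping, so its counts must not be read without the rates and the all-events table beside them.

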Main objectives	
Primary objective:
 
To establish the dose-response relationship of twice daily applications of delgocitinib cream 1, 3, 8, and 20 mg/g and delgocitinib cream vehicle for 16 weeks in the treatment of subjects with mild to severe chronic hand eczema.
 
Other objectives:
 
To compare the safety of twice daily applications of delgocitinib cream 1, 3, 8, and 20 mg/g with delgocitinib cream vehicle for 16 weeks in the treatment of subjects with mild to severe chronic hand eczema.
 
To evaluate the health-related quality of life and efficacy of twice daily applications of delgocitinib cream 1, 3, 8, and 20 mg/g compared to delgocitinib cream vehicle for 16 weeks in the treatment of subjects with mild to severe chronic hand eczema.
 
To evaluate the effect of delgocitinib on Staphylococcus aureus colonisation of the skin, skin microbiome, skin barrier function, and skin inflammation.

Primary endpoint	
 Investigator's Global Assessment (IGA) score of 0 (clear) or 1 (almost clear) with at least a 2-step improvement (IGA treatment success [TS]) from baseline to Week 16.
Secondary endpoints	
 Change in Hand Eczema Severity Index (HECSI) from baseline to Week 16. Time to IGA TS.
Final collection of data for the primary endpoint	Week 16.
Trial design	
The trial is designed as a double-blind, multi-centre, randomised, 5-arm, vehicle-controlled, parallel-group trial in which adult subjects with mild to severe chronic hand eczema will be treated with delgocitinib cream 1, 3, 8, or 20 mg/g or delgocitinib cream vehicle for 16 weeks.
 
The trial consists of a screening period, a treatment period, and a follow-up period.

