Primary objective	
Primary and secondary endpoints
 
Primary endpoint
 
 Investigator's Global Assessment (IGA) score of 0 (clear) or 1 (almost clear) with at least a 2-step improvement (IGA TS) from baseline to Week 16. 
Secondary endpoints
 
 Change in Hand Eczema Severity Index (HECSI) from baseline to Week 16. Time to IGA TS.
Other objectives	
Other endpoints
 
Safety and tolerability
 
 Number of adverse events (AEs). 
Health-related quality of life and efficacy
 
 Change in Chronic Hand Eczema Symptom Diary (HESD) (weekly average for each individual symptom) from baseline to Week 16. 
 Reduction in worst pruritus ("itch" – one of the symptoms captured in HESD) (weekly average) of ≥ 4 points from baseline to Week 16 among subjects with baseline worst pruritus (weekly average) ≥ 4. Change in Chronic Hand Eczema Impact Scale (HEIS) from baseline to Week 16. Patient's Global Assessment (PaGA) TS at Week 16. PaGA TS refers to achieving: PaGA score of 0 (clear) when classified at baseline as 1 (almost clear) or 2 (mild), or PaGA score of 0 (clear) or 1 (almost clear) when classified at baseline as 3 (moderate) or 4 (severe). Time to PaGA TS.

Objectives	Endpoints

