14.3.3 Exposure and treatment compliance

The duration of exposure to treatment in a specific visit interval will be calculated as the number of days from date of first application of IMP in that period to the date of last application of IMP in that period, both days included.

Exposure to treatment will be presented for the safety analysis set as days of exposure per treatment group.

Drug accountability data will be calculated by subtracting the weight of the used tubes from the mean normal weight of full tubes. Average weekly/bi-weekly and total usage will be presented per treatment group, respectively, both for time intervals between visits (1 or 2-week periods depending on the time between site visits) and total period.

Adherence to treatment regimen will be recorded in the eCRF. If any complications or deviations in administration are observed, these will be described as protocol deviations.

Adherence will be presented for the safety analysis set for each treatment group via the percentage of applications missed.

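### The AE tables in Section 14.3.9.1 make no allowance for time under observation, so unequal early loss between arms would by itself shift the comparison with vehicle

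*Combined protocol and SAP*

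**What the plan says.** The synopsis makes the safety objective comparative: "To compare the safety of twice daily applications of delgocitinib cream 1, 3, 8, and 20 mg/g with delgocitinib cream vehicle". The matching endpoint in Section 6, Panel 3 is the number of AEs.

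Section 14.3.9.1 plans "An overall summary of the number of events and the number (percentage) of subjects with any treatment-emergent AEs", followed by tables by type of event: "The number of AEs and number of subjects with each type of AEs will be tabulated by treatment group". Severity, causality, AEs of special interest and AEs leading to withdrawal or to stopping IMP are also tabulated by arm. None of these uses a person-time denominator, a rate or a time-to-event method.

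Three passages fix the period of observation:

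- The treatment-emergent window has a start but no stated end (Section 14.3.9.1): "An event will be considered treatment-emergent if started after the first use of IMP".
- AEs are collected "until completion of the clinical trial for the individual subject" (Section 13.2).
- Section 14.3.3 has a separate table: "Exposure to treatment will be presented for the safety analysis set as days of exposure per treatment group". It counts days on IMP, not days under AE observation, and is not linked to the AE tables.

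On early leavers, Section 10.3 says: "Subjects, who withdraw from the trial must attend an early termination visit as soon as possible after last administration of IMP". Subjects who only stop IMP are asked to attend three visits: early termination, safety follow-up and Week 16. Section 10.1 says that neither group is replaced.

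**The concern.** A percentage of subjects corrects for the size of an arm, not for how long its subjects were watched. A subject who leaves at Week 4 has had about 4 weeks in which an AE could be recorded, and a completer about 18. If loss is equal across arms, the shortfall cancels. If it is unequal, the arm with more early loss shows fewer AEs, and fewer subjects with an AE, even when the true rates are the same.

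Unequal loss is possible here. Lack of efficacy is a listed reason for leaving (Section 10.1), and the sample size assumes success rates of 45% and 15% (Section 14.1). What is at stake is a fair reading of each strength against vehicle in the safety tables. The bias could run in either direction, depending on which arm loses more subjects.

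**Working it through.** **Figures in the plan.** The documents give no expected AE rate and no withdrawal rate. The only design calculation is the power in Section 14.1, for 45% v 15% with 50 per arm at a two-sided 5%. With pooled variance under the null:

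- SE under the null = √(2 × 0.30 × 0.70 / 50) = 0.0917
- SE under the alternative = √((0.45 × 0.55 + 0.15 × 0.85) / 50) = 0.0866
- z = (0.30 − 1.96 × 0.0917) / 0.0866 = 1.39, so power is 91.8%

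This agrees with the stated value of slightly above 90%. It has no bearing on AEs beyond supplying n = 50.

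**Inputs for the illustration**

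- From the documents: n = 50 per arm; full observation T = 16 + 2 = 18 weeks.
- Assumed: withdrawal L of 10%, 20% or 30%; leavers exit either evenly over the 18 weeks (mean 9 weeks) or all at Week 4; the same constant AE hazard in both arms, set so that half of fully observed subjects have an AE, h = ln 2 / 18 = 0.0385 per week.

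**Formulas**

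- Mean weeks observed = 18(1 − L) + mL, with m = 9 or 4
- Expected events = 50 × h × mean weeks
- Subjects with an AE = 0.5(1 − L) + qL, where q is the chance that a leaver has an AE before exit: 1 − 0.5/0.693 = 0.279 (even exit) or 1 − 0.5^(4/18) = 0.143 (Week 4)

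| Exit | L | Mean weeks | Events per 50 | Count relative to L = 10% | Subjects with an AE |
|---|---|---|---|---|---|
| Even | 10% | 17.1 | 32.9 | – | 47.8% |
| Even | 20% | 16.2 | 31.2 | 0.947 (−5%) | 45.6% |
| Even | 30% | 15.3 | 29.5 | 0.895 (−11%) | 43.4% |
| Week 4 | 10% | 16.6 | 32.0 | – | 46.4% |
| Week 4 | 20% | 15.2 | 29.3 | 0.916 (−8%) | 42.9% |
| Week 4 | 30% | 13.8 | 26.6 | 0.831 (−17%) | 39.3% |

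The ratios of counts depend only on the mean weeks, not on the hazard chosen.

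**Other exit times.** With a mean exit at 8 or 6 weeks and 30% v 10% loss, mean observation is 15.0 v 17.0 or 14.4 v 16.8 weeks. The ratios are 0.88 and 0.86, inside the range above.

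**Effect of a person-time denominator.** At 52.18 weeks per year, the even-exit arms with 10% and 20% loss have 50 × 17.1 / 52.18 = 16.39 and 50 × 16.2 / 52.18 = 15.52 patient-years. Both give 200.9 events per 100 patient-years, as does every other row. Under a constant hazard the rate removes the artefact.

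**Size against chance variation.** At 20% v 10% loss with even exit, the difference is 1.7 events. Its Poisson standard error is √(32.9 + 31.2) = 8.0. The percentages differ by 2.2 points (3.5 points with exit at Week 4), against a standard error of about 10 points with 50 per arm.

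**The case against.** The strongest case against is that this is a fixed 16-week trial with descriptive safety tables, in which the effect is small and already partly guarded against. Much of that stands.

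- **Follow-up is wider than Section 10.3 alone suggests.** IMP stoppers are asked back at Week 16 and so keep most of their observation time. Section 7.1 and Panel 2 footnote 4 give all subjects a visit about 2 weeks after the last application. Panel 2 footnote 3 covers withdrawals as well as stoppers and says they will be asked to return at Week 16, but it points to footnote 5, which names only stoppers. A reader might infer that every withdrawn subject is lost after one visit. The documents do not settle that.
- **Fewer visits are a different problem.** After early termination at Week 4, a stopper has 2 scheduled visits left, against 7 for a subject still on treatment. The question at each visit covers the time since the last one (Section 13.2), so this is a matter of how fully AEs are picked up. It is not lost person-time, and a rate does not correct it.
- **A poorly tolerated strength would not go unseen.** An AE that causes withdrawal is itself counted, and AEs leading to withdrawal or to stopping IMP are tabulated by arm. Stinging and burning are summarised separately (Section 14.3.9.4). The exposure table would show an imbalance in treatment duration, though it adjusts for nothing.
- **A reader might infer that dose selection is distorted.** Section 14.3.5 gives that role to MCP-Mod on IGA TS. Section 5.3 says only that the trial's results in general will support it.
- **A reader might also infer that vehicle will lose more subjects and so look safer.** No withdrawal rate is given, so both size and direction are open.

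A separate statistical analysis plan is to be finalised before unblinding (Section 14.3.12). No text from it on AE rates is in the document, and the safety section does not defer to it.

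**Conclusion.** The concern holds in a limited form. Section 14.3.9.1 compares arms by counts and by numbers or percentages of subjects, while the time over which AEs are collected can differ by arm. Under equal constant AE rates, a 10-point difference in withdrawal lowers the crude count by about 5% to 8%, and a 20-point difference by about 11% to 17%. These figures rest on assumed withdrawal shares and exit times. They refer to loss from the trial, not to stopping IMP, and they shrink if AEs cluster early or are the cause of leaving. With equal loss there is no bias.

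No AE test is planned, so the risk is that tables are misread, not that a type I error rate is inflated. A small imbalance in loss would be minor beside chance variation at 50 per arm. The gap is still worth closing, because the stated objective is a comparison with vehicle and the remedy is cheap.

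**What to change.** In Section 14.3.9.1, or in the statistical analysis plan before the code is broken:

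1. Define AE observation time per subject as first IMP application to last trial contact, and state that the treatment-emergent window closes at the same point.
2. Keep the planned counts and percentages. Beside them, add patient-years of observation per arm and AE rates per 100 patient-years.
3. In the overall table, give the rate difference or ratio of each strength against vehicle with a 95% CI. Let the interval allow for repeat events within a subject, for example by robust variance or a negative binomial model, or base it on first events. A simple Poisson interval on all events would be too narrow.

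The cost is a few extra columns. The dates are already collected: AE start dates under Section 13.3, and the last visit or contact on the end of trial form under Section 11.9.

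The limits should be stated with the tables. The rate assumes a roughly constant hazard, it mixes time on and off IMP, and it does not correct for less frequent AE questioning after IMP is stopped. The crude figures should therefore stay beside it.

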Appendix 2: Classification of adverse events

Severity

The *severity* of the AE should be described in terms of mild, moderate or severe according to the investigator's clinical judgement.

Mild	An AE that is usually transient and may require only minimal treatment or therapeutic intervention. The event does not generally interfere with usual activities of daily living.
Moderate	An AE that is usually alleviated with additional specific therapeutic intervention. The event interferes with usual activities of daily living, causing discomfort but poses no significant or permanent risk of harm to the subject.
Severe	An AE that interrupts usual activities of daily living, or significantly affects clinical status, or may require intensive therapeutic intervention.

If the severity of an AE worsens, a new AE should be recorded.

Causality

The *causal relation* of the AE to the use of the IMP should be described in terms of probably, possibly, or not related according to the investigator's clinical judgement. The categories are defined below.

Probably related	
Follows a reasonable temporal sequence from administration of the IMP.
 
Could not be reasonably explained by the subject's clinical state, environmental or toxic factors or other therapies administered to the subject.

	
Follows a known pattern of response to the IMP.
 
Disappears or decreases on cessation or reduction in dose of the IMP.
 
Reappears or worsens upon re-challenge.

Possibly related	
Follows a reasonable temporal sequence from the administration of the IMP.
 
Could also be reasonably explained by the subject's clinical state, environmental or toxic factors or other therapies administered to the subject.
 
Follows a known pattern of response to the IMP.

Not related	
Does not follow a reasonable temporal sequence from administration of the IMP.
 
Is better explained by other factors like the subject's clinical state, environmental or toxic factors or other therapies administered to the subject.
 
Does not reappear or worsen upon re-challenge.
 
Does not follow a known pattern of response to the IMP.

Outcome

The *outcome* of the event according to the investigator's clinical judgement should be classified using the categories below.

Recovered/ resolved	The event has stopped. The stop date of the event must be recorded.

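### Read as written, the causality table lets a later unrelated event of the same preferred term overwrite an earlier related one, and the other related-AE outputs do not say whether they follow that rule

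*Combined protocol and SAP*

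**What the plan says.** Section 14.3.9.1 (Adverse events) first fixes the unit of tabulation: "In each of the tabulations, AEs are defined by MedDRA preferred terms within primary SOC". Separate events with one preferred term in one subject therefore count as one type of AE.

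Two rules then reduce several recordings to one value:

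- For severity, "severity will be taken as the most severe recording for that AE".
- For causality, the rule opens "Where there are several recordings of causal relationship to the IMP for a given type of AE" and continues "causal relationship will be taken as the most-related recording from the last report of that AE". The reason given is "since that is when the investigator will be in possession of most information and so best able to judge causal relationship".

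The section then defines a related AE as any that the investigator has not rated as unrelated, and adds: "The number of subjects with each type of related AE will be tabulated". An overall summary also counts treatment-related AEs. Neither of these outputs mentions the last report.

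Appendix 2 gives three causality ratings (probably, possibly, not related). It also says: "If the severity of an AE worsens, a new AE should be recorded". One subject can therefore have several records under one term.

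**The concern.** The reason given for the causality rule suits one event assessed more than once: the later view is better informed. It does not suit two separate events that share a term. What the investigator learns about an event in Week 14 need not change the judgement about a different event in Week 2. The severity rule in the same section has no such limit, and no reason is given for pooling separate events differently.

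The protocol leaves room for the case to arise. Under section 10.3, subjects who stop the IMP are asked to attend a safety follow-up visit and a Week 16 visit, and the schedule in section 4 collects AEs at both. The treatment-emergent definition in 14.3.9.1 sets no end date. A recurrence after stopping may be rated unrelated, because lack of a plausible time relation to application is part of that category in Appendix 2. Under the rule as written, that rating would replace the one given on treatment.

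At stake is how far the causality table can be read at face value, and whether it agrees with the other related-AE outputs. Comparing safety between strengths and vehicle is a stated objective of the trial.

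**Working it through.** The plan states no figure for this rule, so there is none to reproduce. The check applies the rule to every possible case with two events.

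**Inputs**

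- Unit: preferred term within primary SOC (14.3.9.1).
- Ratings in increasing order: not, possibly, probably (Appendix 2). Related means possibly or probably (14.3.9.1).
- Rule as written: the rating in the last report for that type of AE.
- Comparator: the most-related rating across all events of the term, parallel to the severity rule.

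**Step 1: what the last report refers to.** In the causality sentence, the AE whose last report is used refers back to the type of AE named at the start of the sentence. The severity sentence is built in the same way. Types of AE are preferred terms, so the last report is the last one for the term. No text limits the rule to repeated assessments of a single event.

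**Step 2: enumeration.** One subject has two separate events of one term, each rated once, giving 3 × 3 = 9 ordered pairs.

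| First event | Second event | Rule as written | Most-related | Effect |
|---|---|---|---|---|
| not | not | not | not | none |
| not | possibly | possibly | possibly | none |
| not | probably | probably | probably | none |
| possibly | not | not | possibly | related event lost |
| possibly | possibly | possibly | possibly | none |
| possibly | probably | probably | probably | none |
| probably | not | not | probably | related event lost |
| probably | possibly | possibly | probably | downgraded, still related |
| probably | probably | probably | probably | none |

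Two pairs lose the related event, one is downgraded and six are unchanged. Each of the three affected pairs is classified correctly when its order is reversed, so the outcome depends only on which event came last. The nine pairs are not equally likely, so 2 of 9 is a count of cases and not an expected rate.

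**Step 3: illustration of size, on assumptions outside the documents.** Suppose a subject has two events of one term, each related with probability *q*, independently.

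- P(at least one related) = 1 − (1 − q)²
- P(related, then not) = q(1 − q)
- Share of subjects with a related event who are shown as not related = q(1 − q) / [1 − (1 − q)²]

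| q | At least one related | Related, then not | Share lost |
|---|---|---|---|
| 0.1 | 0.19 | 0.09 | 47% |
| 0.3 | 0.51 | 0.21 | 41% |
| 0.5 | 0.75 | 0.25 | 33% |

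If the two ratings always agree, the share is 0%. For two events per subject, the range runs from 0% under perfect agreement to the figures above under independence. Ratings of the same term in the same subject probably agree more often than independence implies. The denominator is only subjects with two events of one term and at least one rated related. The documents give no figure for how many there would be.

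**Step 4: the other outputs.** If the related-AE table and the overall summary are built from individual events, a subject with probably-then-not counts as related there and as not related in the causality table. If they use the causality table's derived value, the related event disappears from all three. The text does not say which applies.

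**The case against.** The strongest reply is that the sentence can be read more kindly: take the last report of each event, then the most-related rating across events. This fits the stated reason and gives the words about the most-related recording a clear purpose. If only one final report per term counted, those words would do almost nothing. The reading is plausible and may be what was meant. It is not what the sentence says once AEs are defined by preferred term, and a programmer following the text could fairly produce the other result.

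Several further objections stand and limit the point:

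- Appendix 2's new record on worsening is often a continuation of one episode, where using the latest judgement is reasonable. It shows that several records per term can arise, not that separate recurrences will be common.
- Section 11.4.5 keeps stinging and burning out of AE reporting unless serious, and section 14.3.9.4 summarises them separately. Recurrent local reactions of that kind are therefore a poor example.
- The rule applies identically in all five arms, and section 14.3.9.1 specifies no test. Overall AE incidence, severity, SAEs, AEs of special interest and AEs leading to discontinuation do not depend on it. Every AE also appears in the subject listings.

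A reader might infer that treatment-related AEs are understated throughout, or that the comparison across strengths is biased towards no harm. The documents support neither. The loss follows from the text only for the causality table, and between-arm bias would need mixed-causality recurrences to differ by arm, for which there is no evidence.

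**Conclusion.** The point holds in a limited form. As written, the rule can show a subject as not related for a preferred term although an earlier event of that term was judged related. It can also make the causality table disagree with the related-AE table and the overall summary, or carry the loss into them.

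The conclusion rests on reading the last report as the last one for the preferred term, which is the literal sense. It affects only subjects with two or more records of one term and mixed causality. Neither the frequency nor any difference between arms can be determined from the documents, and the percentages in the working are illustrations under assumed probabilities. The consequence is descriptive and touches no efficacy result. It is still worth correcting before unblinding, because a stated rule that can hide a related event is more than a missing detail.

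**What to change.** Replace the causality sentence in 14.3.9.1 with a rule in two steps:

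1. Within each event, use the investigator's final causality assessment.
2. For each subject and preferred term, use the most-related of those assessments across all events of that term.

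State that the same derivation feeds the causality table, the related-AE table and the overall summary of treatment-related AEs. Because Appendix 2 opens a new record when severity worsens, also state whether such a record counts as a new event or as part of the earlier one. Under the two steps, none of the nine pairs in the working loses or downgrades a related event.

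The cost is a sentence or so of text and the matching programming. No new data are needed. Related counts in the causality table may rise slightly.
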